2.0 INTRODUCTION

2.1 Background

2.1.1 Prostate Cancer

In the United States, an estimated 164,690 cases of prostate cancer will be diagnosed in 2018 (Siegel, 2018). However, many of these men will have disease that may never cause morbidity or mortality due to their diagnosis of prostate cancer. Therefore, the management of newly diagnosed, localized prostate cancer detected on the basis of prostate-specific antigen (PSA) remains controversial. Recently, Cooperberg et al. showed a shift from initial active treatment (e.g., surgery, radiation) to choosing AS (Cooperberg, 2015). Active surveillance (AS) delays or indefinitely postpones the complications of surgery, radiation or androgen deprivation therapy (ADT), while allowing for subsequent interventional treatment with similar clinical efficacy associated with immediate treatment (Dall'Era, 2017). Men on AS are advised to adhere to follow-up protocols and schedules (Borkhorst, 2015), yet 25% to 45% of men were no longer on AS after 5 to 15 years of follow-up (Klotz, 2015). The most common reasons for discontinuing AS were PSA-doubling time (43.5%), grade progression (35%) patient preference (6%), and stage progression (3%) (Klotz, 2015). Recently, the PRIAS study investigators concluded Gleason upgrading and disease re-classification (\geq cT3) as the only indicators for an immediate switch to active treatment. Surrogate indicators such as number of positive cores and a PSA-doubling time of <3 years should not trigger immediate active treatment but instead continued follow-up to confirm higher-risk disease (Borkhorst, 2016). Thus histopathologic progression is an important indicator for prostate cancer progression and the need for treatment, and decreasing histopathologic progression would be a significant benefit for the AS prostate cancer population.

2.1.2 Sipuleucel-T

Sipuleucel-T is an autologous cellular immunotherapy available as a suspension for intravenous infusion. Sipuleucel-T consists of autologous peripheral blood mononuclear cells (PBMC), including antigen presenting cells (APCs) that have been activated during a defined culture period with a recombinant human protein, PAP-GM-CSF, consisting of prostatic acid phosphatase (PAP), an antigen expressed in prostate cancer tissue, linked to granulocyte-macrophage colony-stimulating factor (GM-CSF), an immune cell activator. Each dose of

sipuleucel-T contains a minimum of 50 million autologous CD54+ cells activated with PAP-GM-CSF, suspended in 250 mL of Lactated Ringer's Injection, USP.

The active components of sipuleucel-T are autologous APCs and PAP-GM-CSF. During culture, the recombinant antigen binds to and is processed by APCs into smaller peptide fragments. The recombinant antigen is designed to target APCs, and may help direct the immune response to PAP. Minimal residual levels of the intact PAP-GM-CSF are detectable in the final sipuleucel-T product.

The patient's PBMCs are obtained via a standard leukapheresis procedure approximately 3 days prior to the infusion date. Due to the autologous nature of sipuleucel-T, it is important that the patient and physician adhere to the personalized leukapheresis and infusion schedules.

The cellular composition of sipuleucel-T is dependent on the composition of cells obtained from the patient's leukapheresis. In addition to APCs, the final product contains T cells, B cells, natural killer (NK) cells, and other cells. The number of cells present and the cellular composition of each sipuleucel-T dose will vary.

The potency of sipuleucel-T is in part determined by measuring the increased expression of the CD54 molecule, also known as ICAM-1, on the surface of APCs after culture with PAP-GM-CSF. CD54 is a cell surface molecule that plays a role in the immunologic interactions between APCs and T cells, and is considered a marker of immune cell activation.

In-process and final sterility tests are initiated prior to shipping, but the final results are not available for up to 7 days. Sipuleucel-T is released for shipping based on acceptable results from 2-day incubation of the in-process sterility test ([Sipuleucel-T, 2017](#)).

Sipuleucel-T induces robust and long-lived antigen-specific cellular and humoral immune responses that target prostate cancer cells. The magnitude of the immune response correlates with overall survival (OS) in subjects with metastatic castration-resistant prostate cancer (mCRPC) ([Sheikh, 2013](#)).

Sipuleucel-T administered to subjects prior to radical prostatectomy demonstrated both a systemic antigen-specific T cell response and a local response with the recruitment of activated effector T cells into the prostate tumor microenvironment ([Fong, 2014](#)). In subjects with non-metastatic hormone-sensitive prostate cancer, the magnitude of immunoglobulin G responses to antigen was significantly higher, and the magnitude of secondary antibody responses (antigen spread), as well as APC activation was significantly greater when compared to subjects with mCRPC ([Antonarakis, 2017](#)). These data suggest sipuleucel-T may have a more robust anti-cancer effect in non-metastatic hormone-sensitive prostate cancer subjects and the potential to slow or inhibit the development of more aggressive disease requiring treatment for men on AS.

The purpose of this study is to determine if sipuleucel-T will decrease the development of histopathologic progression upon subsequent prostate biopsies for subjects on AS.

3.0 STUDY OBJECTIVES

3.1 Primary Objective

- To assess the efficacy of sipuleucel-T in reducing histopathologic reclassification to a higher Gleason grade in prostate cancer subjects on active surveillance (AS)

3.2 Secondary Objectives

- To assess the differential receipt of local or systemic therapy (surgery, radiation, ADT) in each study arm, and the reasons for receipt of further local or systemic therapy
- To assess differences in quality of life (i.e., patient-reported outcomes (PRO)) between sipuleucel-T and control arms
- To evaluate the safety of sipuleucel-T in men with low to intermediate risk localized prostate cancer

3.3 Exploratory Objectives

- To evaluate in the sipuleucel-T arm the association of peripheral blood and tumor microenvironment immunologic responses with reclassification of Gleason grade over time
- To evaluate clinical assessments and potential correlation to sipuleucel-T
- To evaluate prostate tissue genomics

4.0 STUDY ENDPOINTS

4.1 Primary Endpoint

- Proportion of subjects without histological reclassification (Gleason group upgrade) within 36 months of randomization as determined by Blinded Independent Central Review (BICR)
 - Upgrade is defined as subjects at randomization with either International Society of Urological Pathology (ISUP) Grade Group 1 (Gleason 3+3) upgraded to Grade Group 2 (Gleason 3+4) or higher or subjects at randomization with Grade Group 2 upgraded to Grade Group 3 (Gleason 4+3) or higher.

4.2 Secondary Endpoints

- To determine the number of subjects with subsequent prostate cancer treatment (e.g., surgery, radiation, ADT) in each study arm
- Characterization of PROs by Memorial Anxiety Scale for Prostate Cancer (MAX-PC), Short Form 12 Health Survey (SF-12), The Expanded Prostate Cancer Index Composite

for Clinical Practice (EPIC-CP), International Prostate Symptom Score (IPSS) at baseline and 12-, 24-, and 36-month visits after randomization

- To evaluate safety by determining the incidence of adverse events (AEs), assessing laboratory data for clinically significant laboratory abnormalities and evaluating physical examination (PE) findings in each study arm

4.3 Exploratory Endpoints

- To calculate the correlation of prostate tissue and peripheral immune responses as well as product parameters to sipuleucel-T efficacy
- To determine in the cohort of subjects having a radical prostatectomy the number subjects with an ISUP Grade Group change (up- or down-grade) determined by BICR from radical prostatectomy tissue histology in each study arm
- To measure the percentage of subjects with a negative biopsy at any post- randomization biopsy assessment in each study arm
- To compare the proportion of subjects with clinical risk group progression (e.g., Cancer of the Prostate Risk Assessment (CAPRA) and National Comprehensive Cancer Network (NCCN) prostate cancer risk groups) between study arms
- To calculate Prostate-specific antigen (PSA) velocity from randomization through study completion in each study arm
- To determine the association of prostate cancer tissue genomic profile and sipuleucel-T treatment

5.0 INVESTIGATIONAL PLAN

5.1 Study Design and Duration

This is a multicenter, randomized, open-label study of immunotherapy with sipuleucel-T compared to control subjects followed on AS. The study will enroll subjects being followed by AS and initially diagnosed within 12 months prior to Screening with either ISUP Grade Group 1 or 2 adenocarcinoma of the prostate.

This study consists of 3 phases (see [Section 8.0](#) for more details):

Screening Phase:

The Screening Phase will begin at the completion of the informed consent process and continues until randomization. Screening procedures will be performed up to 30 days prior to randomization.

The following assessments will be performed on all subjects during the Screening Phase:

- BICR of prostate biopsy slides obtained from local pathologist (ISUP Grade Group and Gleason Score)
- Clinical evaluations (demographics, medical history, PE & vital signs, digital rectal examination (DRE), Eastern Cooperative Oncology Group (ECOG) performance status, cardiovascular risk assessment & electrocardiogram (ECG))
- Cardiovascular and thrombosis disease history
- Concomitant medications
- All anti-prostate cancer therapies
- PROs/Quality of life questionnaires
- Virology serology (HBsAg, HBsAb, HBcAb, HCV antibody(Ab), if Ab positive (Ab+) then HCV RNA)), HIV-1 and HIV-2 antibody screen and HTLV-1, HTLV-2 antibodies
- Hematology and chemistry
- PSA
- Total testosterone

Active Phase:

The Active Phase will begin at randomization and continues through completion of the end of Active Phase study visit (within 30 days of Biopsy 2) or until the study is terminated by the sponsor. Subjects who withdraw consent and discontinue from the study prior completing end of Active Phase study visit will undergo an Early Withdrawal visit within 30 days following discontinuation notice ([Section 6.3](#)). Subjects are encouraged to have, as standard of care, a systematic prostate biopsy (≥ 10 cores) with or without MRI at the investigator's discretion prior to study withdrawal. The H&E and special-stained slides from this biopsy will be submitted for BICR determination of their ISUP Grade Group classification prior to study withdrawal

After Screening assessments are completed, eligible subjects will be randomized 2:1 to the sipuleucel-T arm or the control arm. Subjects randomized to sipuleucel-T arm will undergo their first leukapheresis within 60 days of randomization and will receive 3 infusions of sipuleucel-T at approximately 2-week intervals. Subjects randomized to the control arm will be followed on AS as described in the schedule of events ([Table 2](#)).

P17-1 (ProVent) Protocol

Subjects randomized to the sipuleucel-T arm will be evaluated at 0, 2, 4, 6, 10, 14, and 26 weeks following the first infusion for:

- Immune responses (Week 0 prior to first infusion is baseline)
- All anti-prostate cancer therapies
- Concomitant medications
- Adverse events (AEs) and serious adverse events (SAEs) (per reporting requirements for the sipuleucel-T arm) ([Section 9](#))

Subjects randomized to the control arm will be evaluated (office visit or phone) at 3 months following randomization for:

- Survival status
- All anti-prostate cancer therapies
- Concomitant medications
- All AEs and SAEs

Subsequently, all subjects in the sipuleucel-T and control arms will be followed every 6 months from date of randomization for at least 36 months for:

- Immune responses (sipuleucel-T arm only)
- Survival status
- PSA levels (should be collected prior to DRE and biopsy procedures)
- DRE assessments
- Prostate cancer disease progression
- All anti-prostate cancer therapies
- Concomitant medications
- All AEs and SAEs

Note, for subjects randomized to the sipuleucel-T arm, scheduled events for the 26-week visit post first infusion and first 6-month visit post randomization may take place on the same visit and only one set of immune samples need to be collected.

During the Active Phase, all subjects in the sipuleucel-T and control arms will complete:

- PROs/Quality of life questionnaires (Max-PC, SF-12, EPIC-CP, and IPSS) annually (12-, 24-, and 36-month visits) post randomization. PROs/Quality of life questionnaires should be collected prior to any procedures on these specified visits.
- Two (2) systematic biopsies (Biopsy 1 & Biopsy 2; ≥ 10 cores each) will be administered as standard of care. Additional cores may be collected by MRI guidance per investigator discretion; however, MRI targeted cores collected at baseline should be repeated for Biopsy 1 & Biopsy 2 ([Appendix 7](#)).

Biopsy 1 will be administered between 12 and 18 months, and Biopsy 2 will be administered between 33 and 39 months post randomization. All hematoxylin and eosin (H&E) and special stained slides will be assessed for histopathologic grading by BICR. Slides from each biopsy will be considered as a group to determine the ISUP Grade Group as opposed to any single slide. The BICR is blinded to a subject's study arm randomization. BICR will receive the local pathology staining methods and Gleason score. All subject information should be redacted from the local pathology reports and slides. Local pathology reports and slides will be identified only by study subject number. All slides will be returned to the clinical trial site.

Post randomization, central pathology requested formalin-fixed paraffin-embedded (FFPE) tissue blocks identified by study subject number will be sent to the central pathology lab for cutting and slide preparation for immunohistochemistry (IHC) and genomic analysis. All tissue blocks will be returned to the clinical trial site.

Follow-up Phase:

Once a subject from either the sipuleucel-T or control arms completes the end of Active Phase visit, they will enter into Follow-up Phase and will complete Follow-up Phase visits every 6 months starting from their last Active Phase visit. The Follow-up Phase end when the last subject enrolled completes Biopsy 2 and end of Active Phase visit or until the study is terminated by the sponsor. All subjects will be assessed for:

[figure not shown]
- Survival status
- PROs/Quality of life questionnaires
- PSA levels (as available by local laboratory)
- Prostate cancer disease progression
- All anti-prostate cancer therapies
- AEs and SAEs (per reporting requirements for each arm; [Section 9](#))

P17-1 (ProVent) Protocol

Upon completion of the study, if the primary endpoint is met, subjects on the control arm may be offered sipuleucel-T.

The figure below presents a schematic of the study design.

Figure 1: Study Schematic

^a Epstein JI, Am J Surg Pathol, 2017

^b Weeks from **first infusion**; Sipuleucel-T arm only; 26 wk. & 6-mo. visit may occur same day

^c Months from **randomization in both arms**

^d Active Phase ends when the last subject enrolled completes 36-mo. Biopsy and end of Active Phase visit

^e International Society Urological Pathology (ISUP); Grade Group 1 = Gleason 3+3; Grade Group 2 = Gleason 3+4

^f Immunohistochemistry (IHC)

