8.11 Histopathology Assessment

During the Active Phase, subjects will have all H&E and special stained slides and local pathology reports from Biopsy 1 and Biopsy 2, as well as any unscheduled biopsies, assessed for histopathologic grading by BICR. Slides from each biopsy will be considered as a group to determine the ISUP Grade Group as opposed to any single slide. All subject information should be redacted from the local pathology reports and slides. Local pathology reports and slides will be identified only by study subject number. All slides will be returned to the clinical trial site.

Subjects on the Active Phase undergoing a radical prostatectomy will submit H&E and special stained slides from prostate slices for BICR as described above. These will be compared to the ISUP Grade Group determined from previous biopsy. FFPE tissue blocks from the radical prostatectomy as requested by central pathology will be submitted for IHC.

Subjects with an ISUP Grade Group upgrade and who remain on AS (i.e., do not undergo prostate cancer therapy) will remain in the Active Phase and continue per the Schedule of Events (Table 1 and Table 2).

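### The arm-blinded central reader is given the local Gleason score with the endpoint biopsies of an open-label trial, which weakens the independence of the primary-endpoint read

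*Protocol*

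**What the plan says.** Protocol 5.1 describes the trial as follows: "This is a multicenter, randomized, open-label study of immunotherapy with sipuleucel-T compared to control subjects followed on AS". Protocol 4.1 and SAP 7.1 make the primary endpoint the BICR determination of whether the grade group has risen. A rise of one group is enough: Grade Group 1 to 2, or 2 to 3.

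On the central read, Protocol 5.1 first says "The BICR is blinded to a subject's study arm randomization" and then "BICR will receive the local pathology staining methods and Gleason score". The same text is in the protocol synopsis and SAP 6.1. Protocol 8.11 confirms that this covers the endpoint biopsies: "subjects will have all H&E and special stained slides and local pathology reports from Biopsy 1 and Biopsy 2" go to BICR, as do those from unscheduled biopsies. Radical prostatectomy slides are submitted in the same way.

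The only masking rule for this material is "All subject information should be redacted from the local pathology reports and slides", with identification by study subject number.

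**The concern.** Central review is the one safeguard in these documents against assessment bias on the primary endpoint. Its value depends on a grade that owes nothing to anyone who might know the arm. Here the reader does not know the arm, but holds a grade that comes from the site side of an open-label trial. If knowledge of the arm influenced the local grade, and the local grade influenced the central one, part of that influence would reach the primary endpoint despite the blinding.

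The endpoint is sensitive to small shifts in grading. One grade-group step is an event, and Protocol 6.0 allows up to 80% of subjects to be Grade Group 1, where the event turns on whether any pattern 4 is called. A small pull on borderline reads in one arm could change the count, and no planned analysis would show it.

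**Working it through.** **Step 1: what the texts settle and what they leave open.**

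| Question | What the documents say |
|---|---|
| Is the central reader blinded to arm? | Yes (Protocol 5.1, SAP 6.1) |
| Does the reader get the local Gleason score? | Yes, expressly (Protocol synopsis and 5.1, SAP 6.1) |
| Does the local report go with the endpoint slides? | Yes (Protocol 8.11) |
| Does redaction remove the local grade? | No. It covers subject information, and the score is expressly supplied |
| Is the local pathologist blinded to arm? | Not stated |
| Is the central grade recorded before the local grade is seen? | Not stated |
| Is there a second reader or adjudication? | Not stated |
| Is a local-central comparison planned? | No. SAP 12.6.1.3 covers the per-protocol set, last observation carried forward and replaced subjects |

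**Step 2: reproduce the design figure.** Inputs from Protocol 10.1: success 0.70 on control and 0.84 on sipuleucel-T, 150 and 300 subjects, one-sided alpha 0.025, stated power 90%, odds ratio 2.25.

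- Odds ratio: (0.84/0.16)/(0.70/0.30) = 5.25/2.333 = 2.25.
- Power by exact one-sided Fisher test, an unstratified stand-in for the planned exact CMH test: 0.903. Normal approximation: 0.902 with continuity correction, 0.921 without.

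The stated power reproduces.

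**Step 3: illustrate what a one-arm error in the final read would do.** Assume no true effect, with 30% upgrading in both arms. Let *a* be the net share of sipuleucel-T upgrades that the final BICR read misses, with none missed on control. The documents give no value for *a*; the values below are assumptions.

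- Control success: 0.70.
- Sipuleucel-T success: 1 - 0.30 x (1 - *a*).
- Expected upgrades on sipuleucel-T: 300 x 0.30 = 90, of which 90 x *a* are missed.
- Rejection probability: the sum, over all pairs of success counts, of Bin(x_S; 300, p_S) x Bin(x_C; 150, 0.70) for the pairs where the one-sided 0.025 test rejects. Each range runs from the Fisher test to the uncorrected pooled z test.

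| *a* | Missed upgrades (of 90) | Sipuleucel-T success | One-sided type I error |
|---|---|---|---|
| 0 | 0 | 0.700 | 2.0-2.6% |
| 0.05 | 4.5 | 0.715 | 4.1-5.4% |
| 0.10 | 9 | 0.730 | 8.1-10.1% |
| 0.20 | 18 | 0.760 | 23.9-28.0% |

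**Step 4: allow for partial carry-over.** Here *a* is the error in the final central read, not the shift at the site. If BICR takes on only a share *c* of a local shift *s*, then *a* = *c* x *s*. With an assumed *c* = 0.25:

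- *s* = 5%: *a* = 0.0125, success 0.70375, type I error 2.4-3.1%.
- *s* = 10%: *a* = 0.025, success 0.7075, type I error 2.9-3.8%.

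**Step 5: equal anchoring in both arms.** If 10% of upgrades are missed in each arm, success is 0.73 in both and the type I error is 1.9-2.6%, so there is no inflation.

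**The case against.** The best defence is that the central reader grades all the slides of a biopsy as a group, blinded to arm, with subject information removed and only a subject number for identification. The local score is extra information and does not replace that read. For bias to arise, the local pathologist must learn the arm, grade differently because of it, and be followed by the central reader. The documents show none of these links. Site investigators know the arm in an open-label trial, but that does not mean the pathologist does.

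This stands, and it limits the point. A reader might infer that the central read starts from the site's answer, or that its independence is lost. The documents support neither: they give no order of reading, and BICR makes its own determination. A reader might also extend the concern to the screening biopsies, whose local reports also go to BICR under Protocol 8.3. Those reads precede randomization, so there is no arm to bias them.

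The defence does not close the gap. The documents neither prevent the first link nor guard against the last, and they give no reason why the reader needs the local Gleason score to grade the slides.

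**Conclusion.** The concern holds as a weakness in protection against bias. Supplying the local grade lets an arm-related shift in local grading influence the central read of the primary endpoint, and nothing planned would detect it. The documents do not show that such a shift exists, or its direction or size.

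The error rates in Step 3 are scenarios. They assume no true effect, 30% upgrading, 300/150 subjects, an unstratified test, no missing Biopsy 2, and a net error confined to the sipuleucel-T arm. On those terms, about five missed upgrades among 300 men roughly double the false-positive rate. It would be wrong to read 24-28% as this trial's type I error: it requires 18 of 90 sipuleucel-T upgrades to be lost in the central read and none on control. The plan should be changed because the safeguard is cheap, not because bias has been demonstrated.

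**What to change.** For all post-randomization specimens (Biopsy 1, Biopsy 2, unscheduled and early-withdrawal biopsies, and prostatectomy), change the sentence in the protocol synopsis, Protocol 5.1 and 8.11, and SAP 6.1 together, so that no copy contradicts another. BICR should receive the slides, core site labels and staining methods. The local Gleason score and grade group should be either redacted by the site or withheld until the central grade is locked.

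Record the local grade in the eCRF, and add to the SAP a table of local-central concordance by arm.

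Leave the screening submissions in Protocol 8.3 as they are. Stripping diagnosis text there could also remove core-level detail that bears on the eligibility criteria in Protocol 6.1.4.

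The cost is one redaction or sequencing step and one extra table. Sample size, alpha, planned power, the number of readers and subject procedures do not change.
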